**Evaluation of a Portable Isokinetic Knee Training Device for Quadriceps
Rehabilitation in Children with SMA**

Researcher: [name], [name]

Department: Institute of Sports Medicine

Institute: Peking University Third Hospital

Beihang University

Date: December 13, 2024

Unique Protocol ID: 2024-973-02

1 Abstract

This study was an interventional trial with a sample size of six, involving patients with spinal muscular atrophy (SMA) who underwent a seated knee extension rehabilitation program. Participants received rehabilitation intervention using a portable isokinetic training device, and paired t-tests were employed to compare the rate of change in the primary outcome.

2 Main Text

2.1 Research Background and Significance

(1) Spinal muscular atrophy is an inherited degenerative disease that primarily affects the lower motor neurons. It is characterized by the degeneration of nerve cells originating from the spinal cord and brainstem, leading to progressive muscle weakness and atrophy in the limbs. The involvement of the lower extremities is often more severe than that of the upper extremities, and the deep tendon reflexes of the patients are significantly weakened or completely disappeared. Severe cases may lead to death due to respiratory complications. The inheritance pattern of SMA is autosomal recessive, with an incidence of about 1/10000. Based on morbidity, age, and clinical manifestation, the disease can be divided into five types. Type 0 SMA usually occurs in prenatal morbidity and usually dies within a few weeks after birth; Type I SMA is the most common, accounting for about 45%, and the morbidity age is 0 to 6 months. The survival rate of untreated type I SMA children at 20 months is only 8%. This type is one of the main causes of early hereditary death in infants; Type II SMA accounted for about 30%. The age of morbidity was younger than 18 months. The 10-year survival rate was 82%; Type III SMA accounts for about 15%, the morbidity is older than 18 months, the patient may survive to adulthood, and the disease progresses slowly; Type IV SMA is seen in adults. With the development of disease-modifying drugs, the motor function and prognosis of SMA patients have been significantly improved. However, the existing treatment drugs can not cure the disease, and SMA patients still need long-term rehabilitation training and care. The importance of family rehabilitation to the life of children with SMA is self-evident. By adhering to long-term standardized rehabilitation management, the progression of SMA disease can be slowed down, muscle atrophy and bone deformities can be prevented or reduced, the mental health of children can be improved, and their quality of life can be enhanced.

(2) In the process of rehabilitation, because of the advantages of isokinetic training, such as high efficiency and quantitative detection of muscle strength, patients with knee joint diseases are often recommended to use isokinetic muscle training machine for rehabilitation or postoperative functional recovery training. In addition to knee disease, it has also been used for stroke, traumatic spinal cord injury and rehabilitation training

(3) However, the scarcity of rehabilitation training resources and professional physiotherapists and the expensive use of training equipment hinder the promotion and popularization of isokinetic training. In addition, the existing commercial isokinetic training instruments such as Biodex, Cybex and IsoMed are large, heavy and high energy consumption fixed equipment. The multi-occasion rehabilitation training requirement of wearing and training at any time cannot be realized, for occasions such as home travel.

(4) From that point of view of safety, a commercial isokinetic trainer provides a large minimum impedance moment and the joint is fully rigid, Therefore, it is not suitable for rehabilitation training for people with weak muscle strength. A portable and wearable knee joint isokinetic training robot with variable joint stiffness can fit the portability and multi-scene use. Human-computer interaction flexibility requirement. With the energy regeneration technology, the problem of high energy consumption and low energy utilization efficiency can be effectively solved.

This study focused on the rehabilitation effect and evaluation of isokinetic training of lower limbs of SMA patients under the influence of stiffness. SMA patients were trained with a wearable isokinetic training robot for long-term isokinetic training to explore the effect of isokinetic training on the rehabilitation of SMA patients.

2.2 Research Objective

Under the premise of fixed angular velocity and range of motion, the objective is to observe and evaluate the long-term isokinetic rehabilitation training effect on SMA patients under the influence of their stiffness.

2.3 Study Design

2.3.1 Study Population

Inclusion Criteria:

1. Age range: 6-12 years old.
2. Diagnosed with Type II Spinal Muscular Atrophy (SMA).

Exclusion Criteria:

1. Participants with severe comorbidities, implanted medical devices preventing MRI or claustrophobia were excluded from the study;
2. Refusal to provide informed consent or inability to complete the entire study protocol, among other factors;
3. Uncontrolled hypertension (systolic blood pressure ≥ 160 mmHg and/or diastolic blood pressure ≥ 95 mmHg) or congestive heart failure classified as New York Heart Association (NYHA) Class III or IV;
4. Cognitively impaired or unable to comprehend the requirements of study participation.

Withdrawal Criteria:

1. The subject withdraws the informed consent form;
2. Serious violation of clinical clinical study protocol;
3. The investigator believes that it is no longer suitable to continue the clinical Experiment;
4. Death of the subject;
5. The subject was lost to follow-up.

Handling of withdrawal of subjects:

1. All participants who withdraw from the study should retain all source data and files. After the participant withdraws, the researcher should use various forms such as phone calls, emails, etc. to contact the participant as much as possible and inquire about the reasons;
2. Record the time and reason for terminating the clinical experiment in detail on the case report form;
3. The injured due to adverse events must be recorded in the case report form if it is finally judged that there is a causal relationship with the experiment device after follow-up. Participant who terminates the experiment due to adverse events must be followed up until the adverse events are resolved or stabilized.

[figure not shown]
2.3.2 Random and covert grouping methods

None

2.3.3 Intervention

Study protocol:

This trial was conducted with the Department of Sports Medicine at Peking University Third Hospital providing the study site, MRI assessments, and rehabilitation protocol guidance. The Department of Neurology at Peking University Third Hospital was responsible for electromyographic evaluations. Beihang University provided the portable isokinetic training device, maintenance services, database construction, data entry, and analysis. The entire study process lasted for 5.5 months. The study flowchart is shown below:

2.3.4 Outcomes

Primary Outcomes:

Peak torque and work during isokinetic knee extension, cross-sectional area of the quadriceps and electromyographic (femoral nerve conduction) parameters.

Secondary Outcomes:

Knee range of motion, weight and height.

Safety Outcomes:

Skin temperature of the suprapatellar bursa of the knee and knee pain level.

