2.3.5 Sample size

$$N = 2 * \left[\left(t_{\frac{\alpha}{2}} + t_{\beta} \right) * \frac{S}{\delta} \right]^2$$

Given that $\alpha = 0.05$ and $\beta = 0.1$, the critical values $t_{\frac{\alpha}{2}}$ and t_{β} are calculated as:

$$t_{\frac{\alpha}{2}} = 1.96, \quad t_{\beta} = 1.28$$

From the Ref. [18], $S = 16.1$, $\delta = 32.3$. After calculation, we obtained

$$N > 5.21$$

Therefore, the minimum sample size $N_{min} = 6$. In this study, we recruited 6 juveniles with SMA type II.

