2.4 Statically Analysis

All statistical analyses were conducted on data collected from all subjects and performed with the MATLAB R2017b (MathWorks), and Microsoft Excel. Using a paired-sample t-test to analyze the significant difference of data. We consider p-values of less than 0.05 to be statistically significant.

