2.7.1 Scheme modification

If there is no significant difference in the experiment results after the plan sample is included. Based on the existing data in this experiment, the sample size will be estimated. The experiment scheme shall be strictly followed. In case of serious adverse reactions caused by equipment defects, the experiment shall be suspended immediately, the defects shall be evaluated, and the decision as to whether the study can be continued will be subject to further ethical approval.

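### At least four unranked primary outcomes are each tested at p<0.05 with no rule for success; if any one of four suffices, two-sided familywise error is about 10–19% (assumed correlation 0.9 to 0)

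*Combined protocol and SAP*

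**What the plan says.** Section 2.3.4 gives the primary outcomes as "Peak torque and work during isokinetic knee extension, cross-sectional area of the quadriceps and electromyographic (femoral nerve conduction) parameters". No order is given, and the nerve conduction parameters are plural and unlisted, so four is a lower bound.

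Section 2.4 is the whole analysis plan: "Using a paired-sample t-test to analyze the significant difference of data", then "We consider p-values of less than 0.05 to be statistically significant". It contains no multiplicity adjustment, hierarchy, co-primary rule or success criterion, and no other section supplies one.

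Other sections read as if there were one primary outcome:

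- The abstract says "paired t-tests were employed to compare the rate of change in the primary outcome", in the singular and on a rate-of-change scale that section 2.4 does not mention.
- Section 2.3.5 uses one alpha (0.05), one S (16.1) and one delta (32.3), and does not name the variable they describe.
- Section 2.7.1 provides for a further sample size estimate in this case: "If there is no significant difference in the experiment results after the plan sample is included". It does not say which outcome is meant.

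**The concern.** The plan does not fix which result would make the trial positive. There are two natural readings, with different consequences. If one significant outcome is enough, the 5% in section 2.3.5 is not the error rate of the claim. If every outcome must be significant, the error rate is protected but the planned 90% power is not power for that claim. The change scale is also open, which gives a second choice within each outcome.

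This is one arm of six children with no randomised comparison. A single chance p<0.05 among several tests could become the headline, and the plan as written would allow it. The trigger in section 2.7.1 has the same ambiguity: with four or more results, the condition of no significant difference can be met for some outcomes and not for others.

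**Working it through.** **Inputs.** From the plan: at least four primary outcomes (2.3.4); paired t-test at 0.05 (2.4); alpha 0.05, beta 0.1, S=16.1, delta=32.3, N=6 (2.3.5). Two-sided testing is inferred from the alpha/2 and 1.96 in 2.3.5, since 2.4 does not state it. Correlations between outcomes are not in the documents and are assumed, from 0 to 0.9.

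**The plan's own figure.** 2 × [(1.96 + 1.28) × 16.1/32.3]² = 5.216. This matches the stated N > 5.21 and rounds up to 6. The calculation covers one comparison at one alpha.

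**Error if any one outcome suffices.** For independent tests:

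- Two-sided, four tests: 1 − 0.95⁴ = 0.1855.
- Improvement only (2.5% per test), four tests: 1 − 0.975⁴ = 0.0963.
- Two-sided, five tests: 1 − 0.95⁵ = 0.226; six tests: 1 − 0.95⁶ = 0.265.

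For correlated outcomes, paired t-tests with n=6 (5 df) were simulated with equal correlation and 300,000 replicates:

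| Assumed correlation | 0 | 0.5 | 0.8 | 0.9 |
|---|---|---|---|---|
| Any of 4, two-sided | 18.5% | 16.5% | 12.7% | 10.4% |
| Any of 4, improvement only | 9.6% | 8.3% | 6.4% | 5.2% |
| Any of 5, two-sided | 22.6% | 19.7% | 14.4% | 11.5% |
| Any of 6, two-sided | 26.5% | 22.5% | 15.8% | 12.4% |

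The reference value is 5% in the two-sided rows and 2.5% in the improvement-only row. Unequal correlations give a figure inside the range. With torque and work at 0.9, cross-sectional area at 0.5 with each of them, and nerve conduction at 0.2 with all three (assumed), any of four two-sided gives 15.8%.

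**Power if all four must be significant.** Error for that claim does not exceed 5%. Power depends on what S measures, so two cases are shown, with the same standardised change for all four outcomes:

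- *S is the SD of one measurement, before and after uncorrelated.* Standardised change 32.3/(16.1 × √2) = 1.419. Noncentral-t power at n=6 is 0.792 for one outcome. For all four it is 0.393, 0.513, 0.621 and 0.675 at correlations 0, 0.5, 0.8 and 0.9.
- *S is the SD of the change.* Standardised change 32.3/16.1 = 2.006. Power is 0.971 for one outcome. For all four it is 0.890, 0.906, 0.930 and 0.943.

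In the first case one outcome alone already falls short of 90%, so part of that loss is not due to multiplicity.

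**Why limb and time point matter.** One outcome tested twice (say two limbs or two visits, assumed) has any-success error of 9.8%, 9.3%, 8.2% and 7.5% at correlations 0, 0.5, 0.8 and 0.9.

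**What N=6 can detect.** A mean change of 1.67 SDs of the change gives 90% power in one paired t-test at two-sided 0.05.

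**The case against.** The strongest reply is that no passage says one significant outcome is enough, so the inflated rate belongs to a rule the plan never states. That is true, and the figures are conditional on it. The all-four rule is not stated either, and an unadjusted 0.05 with no success rule leaves the choice open until the results are known.

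Second, the two-sided 10–19% counts significant worsening as a success. For a claim of benefit the relevant figures are 5.2–9.6% against 2.5%. This stands as a point of reading. The absolute numbers are smaller, but the rate is still about two to four times its reference.

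Third, the power figures rest on an S and delta whose variable is unnamed, and they apply one effect size to four different measurements. This also stands. They are two scenarios, not bounds: if S is the SD of one measurement and the before-after correlation exceeds 0.5, power is higher than any figure shown. The error rates do not depend on S or delta.

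Fourth, a six-child study whose aim is "to observe and evaluate the long-term isokinetic rehabilitation training effect on SMA patients" can reasonably be read as exploratory. Estimates with intervals for every outcome and no confirmatory claim would then be legitimate. But section 2.3.5 plans 90% power, section 2.4 declares significance and section 2.7.1 acts on it, so the plan as written is not an estimation plan.

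Finally, the study flowchart mentioned in section 2.3.3 may already fix the visits. The fix should draw on it; its content is not being called missing.

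**Conclusion.** The concern holds. The plan names at least four primary outcomes, tests each at an unadjusted 0.05, and does not say which or how many decide the trial, while the abstract and section 2.3.5 assume one.

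If any one of exactly four is enough, two-sided familywise error is about 10–19%, or about 5–10% for improvement against 2.5%, over assumed correlations from 0.9 to 0. Each further nerve conduction parameter raises it. If all four are required, there is no inflation and the open question is power.

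This should be fixed. It affects how any result may be interpreted and is cheap to close, but it does not stop the study.

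**What to change.** 1. **Section 2.3.5.** State which variable and unit S=16.1 and delta=32.3 describe.
2. **Section 2.3.4.** Name one listed outcome as the only primary, with its limb, its assessment time point (from the study flowchart) and its change scale (absolute or rate of change). Make the others secondary, reported as mean change with 95% CI and no confirmatory claim. If S and delta do not describe the chosen outcome, say in 2.3.5 that the stated 90% power does not apply to it, keep N=6, and give the detectable change of 1.67 SDs of the change.
3. **Sections 2.4 and 2.7.1.** Add: *The conclusion, and any finding of no significant difference, refer to the primary outcome only, tested once at two-sided 0.05. A sample size re-estimated under 2.7.1 is for a new study, not for a pooled retest at 0.05.* Section 2.7.1 does not propose such a retest, but it does not say how the existing data would be used.
4. **Date the choice** before the outcome data are analysed. The text is in the past tense ("In this study, we recruited 6 juveniles with SMA type II"; "The entire study process lasted for 5.5 months"). If the data have been seen, label the choice post hoc; naming a primary at that stage discloses the problem but does not restore error control.

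**Alternative if all four stay primary.** Name one nerve conduction parameter, then either use Holm at overall two-sided 0.05 or state that all four must be significant at 0.05. An estimation-only report would also close the gap, provided the significance language in 2.4 and 2.7.1 is removed.

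**Cost.** The main fix changes wording in four sections; N stays 6 and the other outcomes lose primary status. The cost of Holm depends on what S means. In each pair below, the first figure takes S as the SD of one measurement with before and after uncorrelated, and the second as the SD of the change.

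- Only one outcome changes: power for it, at 0.0125, is about 0.47 or 0.80.
- All four change equally: the chance of at least one success is 0.64–0.92 or 0.90–0.998.
- All four change equally: average power per outcome is 0.58–0.62 or 0.88–0.95, against 0.79 or 0.97 unadjusted.

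### As far as the readable plan shows, a paired t-test in one group of six growing children can establish change over the training period but not an effect of the training, and weight and height are given no role in interpreting that change

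*Combined protocol and SAP*

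**What the plan says.** All references are to the combined protocol and SAP.

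- **Design.** The Abstract and 2.3.5 give a sample of six children with type II SMA, all trained on the device. The entry under 2.3.2, on randomisation and concealment, is none. No readable section describes a control arm, an untrained limb, an untrained period or an external comparison. The flowchart announced in 2.3.3 is not in the text available, and 2.3.3 gives 5.5 months for the whole study.
- **Population.** Section 2.3.1 sets "Age range: 6-12 years old". Its criteria say nothing about disease-modifying drugs.
- **Aim.** Section 2.1 says the training is used "to explore the effect of isokinetic training on the rehabilitation of SMA patients". The objective in 2.2 is "to observe and evaluate the long-term isokinetic rehabilitation training effect on SMA patients".
- **Outcomes (2.3.4).** The primary outcomes include "Peak torque and work during isokinetic knee extension, cross-sectional area of the quadriceps", with no scaling for body size, together with femoral nerve conduction. The secondary outcomes are "Knee range of motion, weight and height".
- **Analysis.** Section 2.4 names only a paired-sample t-test, with significance at p<0.05. The Abstract says "paired t-tests were employed to compare the rate of change in the primary outcome", but no section defines that rate or the two values that form the pair.

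**The concern.** If the pair is before and after training, the test takes zero change as what would have happened without training. That is doubtful here, and section 2.1 itself supplies two reasons. It describes the disease as "leading to progressive muscle weakness and atrophy in the limbs", which would pull the outcomes down. It also says "With the development of disease-modifying drugs, the motor function and prognosis of SMA patients have been significantly improved", which could push them up in a child on such a drug. Growth over several months may raise torque, work and muscle area, and practice with the test may raise torque and work. The planned test sees only the sum of these influences and training.

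At stake is the meaning of the headline p-value. Read against 2.2, any change would be credited to, or held against, the device. The p-value also drives a decision: under 2.7.1, a non-significant result leads to a new sample size estimate. Growth is the one competing explanation that the listed outcomes can help to examine, but the plan gives weight and height no part in interpreting torque, work or area.

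**Working it through.** **The plan's own figure.** Section 2.3.5 uses N = 2 × [(1.96 + 1.28) × S/δ]² with S = 16.1 and δ = 32.3. This gives 2 × (3.24 × 16.1/32.3)² = 2 × 2.608 = 5.22. The plan states N > 5.21 and rounds up to 6, so the figure reproduces. It does not bear on attribution, because no term in it stands for change without training.

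**When the planned test is significant.** Inputs: n = 6 (2.3.5), two-sided 0.05 (2.3.5 and 2.4), 5 degrees of freedom, critical t = 2.571. The test rejects when |mean change|/SD of change exceeds 2.571/√6 = 1.05, whatever caused the change.

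**Chance of p<0.05 with no training effect.** Let g be the mean drift from all other causes, divided by the SD of the change. The test statistic is noncentral t with 5 degrees of freedom and noncentrality g√6. The values of g are assumed; none is in the documents.

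| g | g√6 | P(p<0.05), either direction | P(significant gain) |
|---|---|---|---|
| 0 | 0 | 5.0% | 2.5% |
| 0.25 | 0.61 | 8.0% | 7.3% |
| 0.5 | 1.22 | 17.1% | 16.9% |
| 1 | 2.45 | 50.7% | 50.7% |

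Simulation with 200,000 runs at g = 0, 0.5 and 1 gave 5.0%, 17.1% and 50.8%.

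**If the drift is downward.** By symmetry, the chance of a significant gain is the difference between the last two columns: about 0.7% at g = −0.25 (7.96 − 7.29) and 0.1% at g = −0.5 (17.07 − 16.93), against 2.5% with no drift. Net progression would therefore hide a benefit.

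**What g means in practice.** Take an assumed drift of 5%. If the SD of percent change is 5, g = 5/5 = 1; if it is 10, g = 5/10 = 0.5; if it is 20, g = 5/20 = 0.25. The same drift matters much when the children change consistently and little when they vary widely.

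**Effect of scaling on precision.** Percent change in torque per kg is roughly percent change in torque minus percent change in weight. Its SD is √(S² + W² − 2rSW), where S and W are the SDs of the two changes and r is their correlation. The 95% half-width is 2.571 × SD/√6. With assumed S = 5 and W = 4:

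- raw: 5.2 points
- scaled, r = 0: SD = √41 = 6.40, half-width 6.7
- scaled, r = 0.3: SD = √29 = 5.39, half-width 5.7
- scaled, r = 0.5: SD = √21 = 4.58, half-width 4.8

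The scaled interval is narrower once r exceeds W/(2S), here 4/10 = 0.4.

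**The case against.** **The design may contain a comparison that the text does not show.** Comparing rates of change fits two periods or two limbs at least as naturally as one change tested against zero, and shared growth would then largely cancel. The none under 2.3.2 answers a heading on randomisation and does not exclude a within-child comparison. This stands, so the point is conditional: a reader might infer that the study is certainly uncontrolled, but the documents do not establish that.

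**Weight and height are not ignored.** They are secondary outcomes, and 2.4 applies the paired test to the data generally, so growth itself may well be reported. This also stands. What is missing is the link from growth to torque, work and area.

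**The size is assumed.** A reader might infer that growth makes a false positive likely. The documents give no heights, growth rates or SD of change. The 16.1 in 2.3.5 has no stated units or outcome and comes from a trial in anterior cruciate ligament rupture. The 5.5 months covers the whole study, not necessarily the paired interval. Large error rates need a drift that is large relative to its SD, and progression may cancel growth or outweigh it. No particular error rate can be claimed.

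**Small single-group studies are legitimate, and 2.1 and 2.2 speak of exploring and observing.** Agreed; no control arm is being asked for. But both sections still name an effect of training as what is explored or evaluated, and the design as described does not isolate one.

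**Conclusion.** The point holds in conditional form. On the readable text, with no comparator described, the paired t-test supports a statement about change within children over the training period. It does not support the attribution in 2.1 and 2.2. Growth, progression, background drugs and practice remain mixed with training, and the net direction of bias is unknown.

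The figures of about 8%, 17% and 51% for drifts of 0.25, 0.5 and 1 SD show the mechanism only. They rest on n = 6, normally distributed changes, a zero reference value and assumed drifts. They are not estimates of the error rate in this study.

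A reader might also infer that scaling for body size would recover the training effect. It would not: it addresses growth alone, one of four influences, and leaves nerve conduction untouched. The claim should be reworded, and scaling is a useful secondary check. Confidence is medium, because the missing flowchart could show a within-child comparison.

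**What to change.** 1. **Wording (main change).** In 2.1, 2.2 and the conclusion, claim within-child change over the training period rather than an effect attributable to the device. State that growth, progression, background treatment and practice are not separated from training. Several sections are in the past tense, so if data are already collected, mark this as a retrospective clarification.
2. **Analysis (2.4).** Say which two values are paired and what reference value is tested. If the pair is trained versus untrained limb or period, say so, and item 1 can be relaxed accordingly. Add a descriptive sensitivity analysis of peak torque and work per kg and of quadriceps area divided by height squared. Use the weight and height nearest to each assessment, since no section says they were measured at the torque or MRI visits. Show confidence intervals beside the raw results. The analysis gates nothing, and it is labelled post hoc if data are already collected. Ratios are preferable to covariates here, because with six children each covariate costs a degree of freedom (critical t rises from 2.57 to 2.78 for the first).

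**Cost.** A few sentences and a few lines of analysis on outcomes already listed, with no loss of power for the raw test. The claim becomes more modest. Weight scaling may over-correct, for example if a child gains mainly fat. Height may be poorly measured where there is deformity. The scaled interval may be wider or narrower, depending on how weight change correlates with outcome change. For these reasons the raw results stay alongside.

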2.5.1 Definition of Adverse Events (AE) and Serious Adverse Events (SAE)

The definition of adverse events in this experiment is: During the training period and follow-up at the end of the experiment, if the subject experiences knee joint pain without reason, or if there is daily pain but the pain worsens without reason, and there is no improvement after two weeks of the above situation, it is considered an adverse event. If given a certain amount of rest time for recovery and without affecting the observation of therapeutic effects, the experiment can continue. Serious adverse events are those that require hospitalization, extend hospitalization time, disable, affect working ability, cause permanent damage to organ function, endanger life or death, etc. during the clinical experiment. The evaluation of adverse events is divided into five levels: definitely related to training, likely related, possibly related, possibly unrelated, and definitely unrelated. The first three are counted as the incidence of adverse reactions. In case of any serious adverse event or important adverse event, no matter whether it is related to the research intervention or whether the intervention operation has been implemented, it must be reported to the clinical experiment institution and the ethics committee within 24 hours after the occurrence.

Qualification criteria for clinical experiment results:

(1) The relevant data of each subject shall be recorded in the case record form designed according to the requirements of the experiment, and the accuracy and integrity of the data shall be guaranteed, with traceability

(2) Key milestones such as the date of signing the informed consent form, the date of enrollment, and the time of each visit should pay attention to data collection to avoid missing information as much as possible.

(3) The efficacy data recorded during each visit period should be obtained by the subjects strictly following the time window specified in the protocol.

For some subjects who violate the above contents, the main researchers and statistical professionals should discuss and decide the specific treatment measures, and evaluate whether they will have a greater impact on the experiment.

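### Knee skin temperature and measured knee pain level have no child-by-child summary, and the only test that could apply, a paired t-test on six children, cannot flag a rise confined to one or two of them

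*Combined protocol and SAP*

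**What the plan says.** All references are to the combined protocol and SAP.

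- **Section 2.3.4** lists as safety outcomes "Skin temperature of the suprapatellar bursa of the knee and knee pain level". It gives no scale, threshold or summary measure. The flowchart announced in section 2.3.3 is not reproduced in the text available to me, so measurement times may be shown there.
- **Section 2.4** is the whole analysis plan. The method is "Using a paired-sample t-test to analyze the significant difference of data", and the decision rule is "We consider p-values of less than 0.05 to be statistically significant". It covers data from all subjects, does not assign the test to particular outcomes and names no other summary.
- **Section 1 (Abstract)** mentions paired t-tests only for the rate of change in the primary outcome.
- **Section 2.3.5** gives the sample: "In this study, we recruited 6 juveniles with SMA type II".
- **Section 2.5.1** has a rule for the individual child on knee pain. It applies "if the subject experiences knee joint pain without reason, or if there is daily pain but the pain worsens without reason", and if "there is no improvement after two weeks of the above situation, it is considered an adverse event". Each event is graded for relatedness on five levels, and the top three levels form the adverse reaction incidence. Serious or important events are reported within 24 hours.
- **Sections 2.7.1 and 2.7.3** act on single cases: suspension for serious reactions caused by equipment defects, and termination after one serious event related to product quality.

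**The concern.** A mean-difference test suits an average benefit hoped for in the group. For a safety measure in six children the signal is different: a marked change in one or two of them matters even if the rest are unaffected. When the change sits in a few children it raises the standard deviation along with the mean, so the t statistic is capped however large the change is.

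The adverse event rule in section 2.5.1 closes only part of this gap:

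- It is limited to pain without an evident reason. Section 2.5 itself lists joint pain from overtraining and limb discomfort from a badly fitted device as possible risks. Pain put down to such a cause can be read as outside the rule.
- Pain that improves within two weeks is outside it, however severe.
- It does not refer to the measured pain level, a size of change or a worst value.
- It does not mention skin temperature, for which no section gives a per-child criterion or count.

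At stake is how the safety result is read. If the section 2.4 test is applied to these outcomes, a non-significant p-value could be taken as reassurance when the test had no chance of showing otherwise.

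**Working it through.** **The plan's own figure.** From section 2.3.5, N = 2 × [(1.96 + 1.28) × 16.1 / 32.3]² = 5.216, rounded up to 6. The stated minimum of 6 reproduces. The planning values concern efficacy and say nothing about safety.

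**Inputs.** n = 6 (section 2.3.5); paired t-test at 0.05 (section 2.4). Sidedness is not stated; two-sided is inferred from the α/2 in section 2.3.5. One value per child is assumed, because the unit (child or knee) is not stated. The critical value on 5 df is 2.571 two-sided and 2.015 one-sided.

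**Bound.** Let d be each child's change, with worsening positive. Then

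t² = (n − 1)(Σd)² / [nΣd² − (Σd)²].

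If k children worsen and the others do not change, the Cauchy–Schwarz inequality gives (Σd)² ≤ kΣd². Hence

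t_max = √[(n − 1)k / (n − k)] = √[5k / (6 − k)],

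reached when the k changes are equal. The size of the change cancels out. Improvement in the other children lowers t further.

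| Children worsening | t_max | p, two-sided | p, one-sided |
|---|---|---|---|
| 1 of 6 | √(5/5) = 1.000 | 0.363 | 0.182 |
| 2 of 6 | √(10/4) = 1.581 | 0.175 | 0.087 |
| 3 of 6 | √(15/3) = 2.236 | 0.076 | 0.038 |
| 4 of 6 | √(20/2) = 3.162 | 0.025 | 0.013 |

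A random search over unequal worsening in three children, with no change or improvement in the other three, found no t above 2.236.

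**Examples.**
- One child goes from 0 to 8 on an assumed 0–10 pain scale and five are unchanged: mean 1.333, standard error 1.333, t = 1.00, p = 0.36.
- Three children rise by 7, 7 and 5 and three are unchanged: t² = 5 × 361 / (6 × 123 − 361) = 4.79, t = 2.19, p = 0.080.
- Four children worsen unequally (1, 2, 3, 6, 0, 0): p = 0.084, so even four of six can be missed.

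**Where the bound gives way.**
- One-sided test: three of six can reach p = 0.038; one or two still cannot.
- Slight rise in the others: changes of 1, 1, 1, 0.1, 0.1, 0.1 give t = 2.73, p = 0.041.
- Twelve knees entered as separate units (best case, two-sided): six worsening knees give p = 0.007 and four give p = 0.039. One child with both knees affected (p = 0.166) or three children with one knee each (p = 0.082) are still missed.

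**The case against.** The strongest reply is that safety is not judged by a t-test at all. The Abstract ties the test to the primary outcome, section 2.4 never assigns it to the safety outcomes, and no section says that a non-significant mean change is the safety result. Section 2.5.1 already works child by child for knee pain and yields an incidence, and sections 2.7.1 and 2.7.3 respond to single cases.

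Much of this stands. A reader might infer that neither safety outcome has any individual criterion, or that half the children could be harmed and the trial would report nothing. The documents do not support either reading. Three children with persistent unexplained knee pain would be recorded as three adverse events whatever the p-value, and would enter the adverse reaction incidence if judged at least possibly related. Nor do the documents say that harm confined to a minority is what this device is most likely to cause.

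The reply does not remove the gap. If section 2.4 covers the safety outcomes, the test cannot see change in one or two children under the conditions shown. If it does not, the two outcomes have no stated analysis. In both cases skin temperature has no individual reading, and the measured pain level is used only as a group mean or not at all. Sections 2.7.1 and 2.7.3 concern serious reactions or events and serious deviations in conduct, not these measurements.

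**Conclusion.** The point holds in limited form. Skin temperature has no per-child reading anywhere. Knee pain level, as measured, has none beyond the adverse event rule for unexplained pain lasting two weeks. A two-sided paired t-test with one value for each of six children cannot reach p < 0.05 for a rise confined to one, two or three of them when none of the others rises (best case p = 0.36, 0.17 and 0.076).

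The three-child result depends on the test being two-sided. The one- and two-child results hold for either sidedness, still with one value per child and no rise in the others. So a non-significant result on these outcomes is uninformative about harm to individual children. That is a statement about the t-test, not about the trial's safety reporting as a whole. I class it as a cheap improvement.

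**What to change.** In section 2.4, with a cross-reference from section 2.3.4:

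1. State that the safety outcomes are not judged by the p < 0.05 rule.
2. For each of the six children, list baseline, every later value and the worst later value of knee pain level and skin temperature, naming the pain scale used and how the two knees are handled.
3. Report the number of children who worsen (x/6, with an exact 95% confidence interval) by a per-child criterion that the investigators fix before analysis. The interval keeps the claim modest: even 0/6 has an upper limit of 1 − 0.025^(1/6) = 0.459, or 46%.
4. Present this beside the adverse reaction incidence from section 2.5.1.
5. State that a non-significant mean change is not evidence of safety.

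The cost is a few sentences and one listing from measurements the plan already calls for. The small downside is that the safety statement becomes descriptive and may look less favourable.
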